BACKGROUND: Hemiparesis, spasticity and reduced motor control are typical impairments after stroke and commonly contribute to motor deficits that affect gait. These deficits manifest as reduced velocity, decreased cadence and asymmetries in temporal, spatial and force parameters during ambulation. Robotic-based therapies have been used to increase gait velocity and reduce asymmetry in a population of individuals after stroke, however these therapies have demonstrated results similar to that of conventional training. This is possibly due to guided-assist control strategies used to deliver robotic training, which strategies limit participant involvement and thus constrain motor learning.

The TPAD is a robotic device that employs actuated tethers at the user's pelvis to guide the user's pelvis along a pre-set movement trajectory. The TPAD tethers can be configured in an infinite array of possibilities, and most recently have been used to increase loading onto the paretic limb in a population of individuals after stroke. While other robotic devices guide the limb through the motor trajectory, and constrict the participants ability to participate in the motor planning and movement execution, the TPAD promotes weight shifting, but allows an individual to freely move the limb and to navigate spatiotemporal aspects of training independently. Further, if coupled with overground to focus on addressing a specific task goal, this device may prove useful to improve symmetry in individuals after stroke.

OBJECTIVES: The purpose of this study is to evaluate the overall feasibility in terms of safety, treatment tolerance and adherence as well as address preliminary efficacy of implementing a treatment paradigm using the TPAD with visual feedback and overground training to reduce load asymmetry on the treadmill and promote increased stance symmetry on the paretic limb during overground gait.

PARTICIPANTS: To account for 20% attrition, a total of 12 individuals in the chronic (>6 months) stages post stroke will be recruited from a voluntary stroke research registry with anticipation that 10 individuals will complete participation.

DESIGN: A non-randomized pilot study of feasibility will be used to establish the preliminary efficacy of using the TPAD in combination with overground training to reduce load force asymmetry in this population.

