METHODS: Participants will undergo a series of three assessments within a one week time frame prior to initiating intervention. Intervention using the TPAD and overground training will occur the following week for five consecutive visits. On completion of the final training visit, participants will be re-assessed, and return for a single follow up visit the next week for the final assessment. Each study visit will be approximately 1-1.5 hours in duration, and total participation should be completed within three weeks.

EXPECTED OUTCOMES: We anticipate this training paradigm will prove feasible in reducing both load and stance asymmetry in a population of individuals with chronic stroke.

II. Research Questions:

- 1) Is a five day gait training program using the TPAD and incorporating augmented visual feedback and an overground walking component feasible in terms of safety, treatment tolerance, and adherence in individuals with chronic stroke who present with gait asymmetry?
- 2) Is this training program effective at improving load force symmetry after five sessions?
- 3) Is this training program effective at improving stance time symmetry in overground gait?

III. Study Design/Methodology

This is a single arm, non-randomized pilot study of feasibility. The study population and details of study procedures are specified below.

IV. Outcome Measures

A. Primary Outcomes

- Measures of Feasibility
 - Safety
 - Adverse Events / Serious Adverse Events
 - Adherence
 - Attendance Rates of Study Visits
 - Tolerance
 - Ratings of Perceived Exertion (RPE)
 - Heart Rate (HR)
- Efficacy
 - Overall Load Force Symmetry (over the course of training)
 - Stance Time Symmetry

B. Secondary Outcomes

- Daily Load Force Symmetry (intraday changes in load force)
- Time in Double Support
- Swing Time Symmetry
- Stride Length Symmetry
- Stride Velocity Symmetry
- Gait Velocity
- Balance (as per the Berg Balance Scale)

V. Study Population

A total of 12 adults (ages 18-75) will be recruited for participation from a voluntary stroke registry, anticipating 20% attrition, or that at least 10 participants will meet criteria and complete study participation.

Inclusion Criteria:

- Chronic (>6 months) stages post stroke
- History of a single stroke event (either ischemic or hemorrhagic by origin)
- Minimal score of 22 or higher on the MoCA
- Must be independent community ambulator (with/without AFO)
- May use a unilateral assistive device (cane, quad cane)

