### **SPECIFIC OBJECTIVES:**

1) Is this five-day intervention using the TPAD and incorporating faded visual feedback and overground walking feasible in terms of safety, treatment tolerance and adherence in individuals with chronic stroke who present with gait asymmetry?

As a measure of treatment efficacy, this study will specifically address the following questions:

2) Is this treatment paradigm effective at improving load force symmetry over the course of five training sessions as measured from Baseline Day one to Post Training Day five?

3) Is this training paradigm effective to promote transfer and improve stance time symmetry in over ground gait as measured from a mean of the three days in Pre Testing to Post Testing?

The presence of preliminary efficacy in the prior two questions, coupled with measures of safety, treatment tolerance and adherence will be used to answer the over arching question of feasibility and preliminary efficacy.

[figure not shown]

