### **Study Design**

We will conduct a single arm, pre / post study with a series of three baseline (Pre-Test) measures, a single post assessment (Post-Test) and a one-week follow up assessment (Follow up). Feasibility measures (in terms of adherence, tolerance and safety) will also be recorded. The availability of feasibility measures is critical for planning future, long-term, randomized controlled trials. Based on prior work, force symmetry can be improved with TPAD training. However, we offer that the integration of a task specific overground training component will

allow individuals to improve transfer of force symmetry into spatiotemporal gait parameters that may ultimately impact gait speed, gait function and quality of life. See Figure 1 for a detailed study schema.

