### **Sample size justification**

This is a pre/post pilot with a one week follow up using multiple baseline (Pre-Test) measures to establish a baseline level of function and variability of gait. Results from this study will be used to calculate sample size for future, larger trials in this population.

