## **Statistical Analyses**

Statistical assumptions and normality will be tested prior to running statistical analysis for measures of treatment tolerance, force symmetry, spatiotemporal gait parameters including stance symmetry and balance. A *p value* of 0.05 or lower will be considered statistically significant for all analyses.

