### ***2.2.2 Stance Time Symmetry Ratio***

Descriptive values (mean (SD)) of stance symmetry will be included in the final report. Mean values of Stance symmetry ratios will be analyzed using repeated measures ANOVA to first compare the relationship of the multiple pre-test measures. If there is no significant difference between the multiple pre-test measures, then the mean of the pre-test measures will be compared to measures at post-test and follow up also using a repeated measures ANOVA. Bonferonni corrections will be used to control for multiple comparisons. The F value and statistical significance will be reported with 95% confidence intervals and effect sizes. A graphical representation of the data will also be reported.

Secondarily, a linear regression model of daily change over time will be created using change scores from the mean of the three Pre Test measures to Day 1 of training. Within day changes for each of the five training days and changes from daily Pre Testing and from daily Post Testing will also be examined with a regression over time. Results of the regression models will be used to determine the presence of a significant change over the course of the intervention and will be reported with the corresponding slope.

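### Stance co-primary: a non-significant ANOVA of the three Pre-Tests is sufficient grounds to average them, but with about 10 people it has little power to detect modest drift, part of which then enters the Pre-to-Post gain

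*SAP*

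**What the plan says.** The SAP's Study Design section describes one arm with "a series of three baseline (Pre-Test) measures, a single post assessment (Post-Test) and a one-week follow up assessment". Its Sample size justification gives the purpose of the repeated visits: "multiple baseline (Pre-Test) measures to establish a baseline level of function and variability of gait". Specific objective 3 defines the overground stance question "as measured from a mean of the three days in Pre Testing to Post Testing".

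SAP 2.2.2 sets the analysis. Stance ratios "will be analyzed using repeated measures ANOVA to first compare the relationship of the multiple pre-test measures". The next step depends on that result: "If there is no significant difference between the multiple pre-test measures, then the mean of the pre-test measures will be compared" with Post-Test and Follow up in a second repeated measures ANOVA, with Bonferroni correction. The Statistical Analyses section sets the threshold: a p value "of 0.05 or lower will be considered statistically significant for all analyses".

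No margin, power or interval is given for change across the Pre-Tests. Section 2.2 of the Statistical Analyses adds visual inspection with celeration lines and 2-SD bands, and 2.2.2 adds secondary regressions of daily change. Neither has a decision rule for the baseline.

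**The concern.** With no control arm, a change in stance symmetry that would have happened without training can be separated from a training effect only through the untrained measurements. The plan uses the three Pre-Tests for this through a significance test: if no difference is detected, they are averaged. A non-significant result in about 10 people may mean that the baseline is flat, or that the test could not see the slope.

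If the ratio is still rising, the mean of the three Pre-Tests lies below the last untrained value, and the gap is carried into the Pre-to-Post gain. Two features of the design make a rise plausible, although neither shows that one occurs. The same instrumented walk is repeated at each Pre-Test and again before and after every training session. Eligibility also requires a ratio of 0.90 or less after Day 1 of Pre Testing, so regression to the mean could lift later visits.

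At stake is one of the two primary efficacy outcomes: transfer to overground gait.

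**Working it through.** **Inputs from the documents.** The Protocol recruits 12, "with anticipation that 10 individuals will complete participation". Check: 12 × 0.80 = 9.6, about 10. Neither document gives power for the Pre-Test check, so there is no figure of the plan's own to reproduce for it. Alpha is 0.05. The stance minimal detectable change (MDC) is 0.09 (SAP, text to Figure 1).

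**Assumptions.**
- Within-person visit SD: the MDC's confidence level is not stated. If 95%, SD = 0.09/(1.96 × √2) = 0.0325. If 90%, SD = 0.09/(1.645 × √2) = 0.0387.
- Drift: linear over the three Pre-Tests, total D. No document gives D, so a range is used.
- Independent visit errors, sphericity, no training effect.

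**Step 1: power of the check.** The test is F with 2 and 2(n − 1) = 18 df; the 5% critical value is 3.55. For linear drift the means are 0, D/2 and D, so the noncentrality is λ = n × D²/(2 × SD²). At n = 10, λ = 1.25 for D = 0.5 SD and 5.0 for D = 1.0 SD. The miss rate is the noncentral F probability below 3.55.

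| Total drift D (SD) | On the ratio scale (SD 0.0325) | Missed, n = 10 |
|---|---|---|
| 0.25 | 0.008 | 93% |
| 0.5 | 0.016 | 86% |
| 0.75 | 0.024 | 74% |
| 1.0 | 0.0325 | 56% |
| 1.25 | 0.041 | 37% |
| 1.5 | 0.049 | 21% |
| 2.77 (D = MDC of 0.09) | 0.09 | under 1% |

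At n = 12 the check misses 84% (0.5 SD) and 48% (1.0 SD). It reaches 80% power only at about 1.51 SD: 0.049 on the ratio scale, or 0.059 with the larger SD.

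**Step 2: bias from averaging.** The Pre-Test mean sits at D/2.
- Drift stops at Pre-Test 3: Post-Test is at D, so the bias is D − D/2 = D/2. For 0.5 and 1.0 SD this is 0.008 and 0.016, or 9% and 18% of the MDC.
- Drift goes one step (D/2) further: Post-Test is at 1.5D, so the bias is D, or 0.016 and 0.0325.

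**Step 3: false-positive rates in the planned analysis.** Simulated trials (n = 10, no training effect, Follow up at the Post-Test level), restricted to those that pass the check. Bonferroni is taken over the three pairwise comparisons of Pre-mean, Post-Test and Follow up. Drift is in SD units, so the choice of SD does not alter these rates.

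| Total drift | After Pre-Test 3 | Pre-mean to Post, Bonferroni | Omnibus F |
|---|---|---|---|
| None | – | 1.6% | 5% |
| 0.5 SD | stops | about 4% | about 9% |
| 0.5 SD | one more step | about 11% | about 21% |
| 1.0 SD | stops | about 10–11% | about 20% |
| 1.0 SD | one more step | about 47% | about 71% |

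**Step 4: Pre-Test 3 as reference.** In the same passing trials, Post-Test minus Pre-Test 3 (paired t, two-sided 0.05, uncorrected) is significant in 4% and 8% at 0.5 SD, and 4% and 22% at 1.0 SD (stops; one more step). The standard error ratio to the Pre-mean contrast is √(1 + 1)/√(1 + 1/3) = 1.414/1.155 = 1.22.

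**The case against.** The strongest reply has five parts.

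- **The drift is assumed.** No document shows an upward trend, and a downward one would hide benefit. This stands. A reader might take miss rates of 56% to 86% as a property of the plan; they belong only to assumed drift of 0.5 to 1.0 SD.
- **The SAP does not claim proof of stability.** Correct. A reader might infer that the plan declares the baseline stable or equivalent. It does not; it only makes averaging conditional on no significant difference.
- **The Bonferroni correction blunts the effect.** Correct for the contrast that answers objective 3. An uncorrected paired t test would give about 9%, 23%, 23% and 68% for the four drift settings, but that is not the planned test. At 0.5 SD with drift stopping, the corrected rate is below 5%, although still more than twice its no-drift value of 1.6%. The correction does not remove the bias from the estimate.
- **Other looks at the baseline exist.** Celeration lines are planned, and the walk before the first training session is a further untrained value that enters a secondary regression. So the three Pre-Tests are not the only information on pre-training trend. These looks lack a rule that would alter the primary comparison or its wording.
- **This is a feasibility pilot, and averaging baselines gains precision.** Both are fair. They argue for keeping the averaged contrast and adding to it, which is what is proposed.

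**Conclusion.** The point holds in limited form. A non-significant three-level ANOVA in about 10 people is the only stated condition for averaging the Pre-Tests, and it cannot distinguish a flat baseline from drift of up to about 1 within-person SD. When it passes despite upward drift, the bias is modest if drift stops (0.008 to 0.016 for 0.5 to 1.0 SD) and twice that with one further step. The corrected contrast's false-positive rate moves from 1.6% to between about 4% and 47% over the settings examined.

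These sizes rest on an assumed linear drift, independent visit errors, Bonferroni over three comparisons and, for ratio-scale values only, a 95% MDC. A reader might infer that all the drift is counted as training benefit. The documents do not support this: half is counted if drift stops at Pre-Test 3, and the full amount or more only if it continues. Nor do they support the reading that large drift would escape: drift equal to the MDC is missed less than 1% of the time.

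The change is worth making before analysis. It does not invalidate the trial.

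**What to change.** In SAP 2.2.2:

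1. Stop treating p > 0.05 as evidence of a stable baseline. Report the Pre-Test 1 to Pre-Test 3 change with its 95% confidence interval whatever the ANOVA result. At n = 10 the expected half-width is 2.262 × 0.0325 × √2/√10 = 0.033 (0.039 with the larger SD), so the reader will see how much drift cannot be excluded.
2. Pre-specify Post-Test minus Pre-Test 3, with its 95% confidence interval, as a sensitivity contrast beside the planned Pre-mean contrast.
3. State that a Pre-mean gain not supported by the size and interval of the Pre-Test 3 contrast will be described as possibly due to pre-training drift. Agreement in direction alone is not enough: the two contrasts share the Post-Test value, and about 98–99% of the false-positive gains in the simulations agree in sign.

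The cost is SAP wording and one contrast from data already being collected. The Pre-Test 3 contrast is less precise (standard error about 22% larger), and it reduces but does not remove bias from drift that continues into the training week.

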#### **2. Efficacy**

There will be two primary measures of preliminary efficacy. First, we aim to establish treatment efficacy on the treadmill. Additionally, we aim to determine whether individuals will

be able to transfer gains to improve symmetry in over ground parameters. Specific outcomes are as follows:

**2.1** The primary outcome measure for efficacy of training on the treadmill will be the calculated load force symmetry ratio as measured load force recorded during Baseline and Post Training on the treadmill with embedded force plates.

**2.2** The primary outcome measure for efficacy of transferability will be the stance symmetry ratio calculated from percentage of time in spent in stance phase of the gait cycle. This will be extracted from data provided by APDM® inertial sensors and measured by the mean of the Pre Test visits to Post Testing.

**2.3** Secondary measures of preliminary force efficacy will include within day changes in load force symmetry as taken on the treadmill. As secondary outcomes to evaluate for transfer of the intervention to overground gait, APDM® inertial sensors will be used to record the percentage of time spent in double support, time in swing phase, stride length, and stride velocity. Symmetry ratios will be calculated for percentage of time in swing phase of the gait cycle, and stride length. Gait velocity as a measure of time performing the 10MWT will also be recorded. Lastly, as an additional balance measure, we will also use the total score of the Berg Balance Scale (BBS).

See Table 1 for a detailed list of measures recorded.

Table 1. All outcome variables and time points at which they will be measured.

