#### ***2.2.1 Load Force (Fz)***

Mean values of Fz Symmetry Ratios will be compared over the course of the five-day training. Specifically, after normality is tested, either a Wilcoxon Signed Ranks test or a paired t test will be used to examine ratio values from the mean of Baseline Day one

to Post Training Day 5. These values will be reported with the associated level of significance. Effect sizes and 95% confidence intervals will also be calculated and reported in the final report. Results will also be presented graphically.

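### The stance primary is defined as one contrast (Pre-Test mean to Post-Test), but SAP 2.2.2 analyses it with a three-level ANOVA and Bonferroni without naming the deciding test or the comparisons corrected for

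*SAP*

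**What the plan says.** The SAP states the stance question twice, each time as one comparison. Specific Objectives, question 3, asks whether training will "improve stance time symmetry in over ground gait as measured from a mean of the three days in Pre Testing to Post Testing". Study Outcomes, 2.2, says the stance ratio is "measured by the mean of the Pre Test visits to Post Testing". Neither mentions Follow Up. Stance is one of two primaries for efficacy: "There will be two primary measures of preliminary efficacy".

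The analysis in 2.2.2 is wider. Once a check on the three Pre-Tests shows no significant difference, "the mean of the pre-test measures will be compared to measures at post-test and follow up also using a repeated measures ANOVA". It continues: "Bonferonni corrections will be used to control for multiple comparisons". The F value is to be reported with its significance, 95% confidence intervals and effect sizes.

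The general rule under Statistical Analyses is: "A *p value* of 0.05 or lower will be considered statistically significant for all analyses". The other efficacy primary, load force, has one paired comparison in 2.2.1: "either a Wilcoxon Signed Ranks test or a paired t test will be used to examine ratio values from the mean of Baseline Day one", ending at Post Training on Day 5. No Bonferroni correction is named there.

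**The concern.** The test does not match the outcome. A three-level F test asks whether any of the three means differ, which is not Question 3. It can be significant because of Follow Up alone. It can also be non-significant when the Pre-to-Post change would have been significant by itself.

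Section 2.2.2 does not say which result settles the question: the F value, the adjusted Pre-to-Post comparison, or both. It also does not say whether Bonferroni covers two comparisons (Post-Test and Follow Up, each against Pre) or all three pairs. The same data could therefore give different answers to a primary question, and the choice could be made after the results are known.

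Whichever family is meant, the correction takes alpha from the contrast the objective names and spends it on contrasts the objective does not name. About 10 completers are expected, so there is little power to spare.

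**Working it through.** **Inputs from the documents.** The protocol's Participants paragraph says "To account for 20% attrition, a total of 12 individuals in the chronic (>6 months) stages post stroke will be recruited", with 10 expected to complete. That is the only sample-size figure, and it is consistent to rounding: 12 × 0.8 = 9.6, and 10/0.8 = 12.5. There is no stated power to reproduce. Alpha is 0.05.

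**Assumptions.** Tests are two-sided (the SAP does not say). The standardised change dz (mean change divided by SD of change) is varied, because the SAP gives no target effect or SD of change. Its one stance figure, a minimal detectable change of 0.09, is used for eligibility. A change of 0.09 would mean dz 1.5, 1.0 or 0.5 if the SD of change were 0.06, 0.09 or 0.18.

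**1. Does the F test answer Question 3?** Take n = 10, sphericity, and an SD of 1 for each paired difference, so the error variance is 0.5. Suppose Pre and Post-Test are equal and only Follow Up shifts by 1. The means are 0, 0, 1 and the squared deviations sum to 2/3. The noncentrality is 10 × (2/3)/0.5 = 13.3. Against the 5% critical value of F on 2 and 18 df (3.55), power is 86%. F would usually be significant with no Pre-to-Post change at all. Conversely, with dz 1.0 at Post-Test and half of it kept at Follow Up, the noncentrality is 10 × 0.5/0.5 = 10. F then has 74% power, below the 80% of the direct test.

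**2. Power for Pre to Post, paired errors.** Power is P(|T| > t(1−α/2, n−1)), where T is noncentral t with n−1 df and noncentrality dz × √n. At n = 10 the critical values are 2.262 (α = 0.05), 2.685 (0.05/2 = 0.025) and 2.933 (0.05/3 = 0.0167).

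| dz | Direct, 0.05 | Two corrected | Three corrected | Loss in points (two / three) |
|---|---|---|---|---|
| 0.3 | 13.6% | 7.9% | 5.7% | 6 / 8 |
| 0.5 | 29.3% | 19.2% | 14.6% | 10 / 15 |
| 0.8 | 61.6% | 47.5% | 39.7% | 14 / 22 |
| 1.0 | 80.3% | 68.2% | 60.4% | 12 / 20 |
| 1.2 | 92.0% | 84.2% | 78.3% | 8 / 14 |
| 1.5 | 98.7% | 96.4% | 94.0% | 2 / 5 |

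The loss peaks at about 14 points (two) or 22 points (three), both near dz 0.8. With three comparisons it is 18 points or more only for dz of about 0.60 to 1.07. For 80% power, dz must be 1.00 (direct), 1.14 (two) or 1.22 (three). If all 12 complete and dz is 1.0, power is 88.3%, 79.3% and 72.9%, so the losses are 9 and 15 points.

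**3. Pooled ANOVA error.** If the comparisons use the ANOVA error term (18 df at n = 10) and sphericity holds, power at dz 1.0 is 75.7% (two) or 69.6% (three). Against 80.3% for the direct paired test, the losses are about 5 and 11 points.

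**4. Interval width.** If the intervals were also Bonferroni-adjusted at n = 10, the width ratios would be 2.685/2.262 = 1.19 (two) or 2.933/2.262 = 1.30 (three).

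**The case against.** The strongest reply is that 2.2.2 is a conventional analysis of a design that includes a one-week follow-up, and that correcting for several time points is cautious and not wrong. The study is a single-arm pilot whose chief purpose is feasibility. It has no power target, and effect sizes are to be reported whatever the p value. Read literally, 2.2.2 compares the Pre mean with two later measures, which points to two comparisons and the smaller loss.

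Much of this stands, and it limits the size of the point. A reader might infer that the plan tests at 0.05/3, compares Post-Test with Follow Up, requires a significant F first, and so gives up a flat 20 points of power with intervals 30% wider. Section 2.2.2 states none of these. It gives no family size, makes no Post-Test versus Follow Up comparison explicit, sets no F gate, and does not say that its 95% intervals are adjusted. The 20-point figure needs three comparisons, about 10 completers, paired errors and a mid-sized effect. The pooled-error figures are conditional too: sphericity is doubtful because Pre is a mean of three visits and the other two levels are single visits.

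The reply does not remove the mismatch. The SAP calls stance a primary, applies the 0.05 rule to all analyses, and uses the answer to Question 3 in its overall judgement of feasibility and preliminary efficacy. Follow Up can be analysed without making it part of the test of Question 3.

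**Conclusion.** The point holds as a mismatch between a one-contrast primary and a three-level analysis, with neither the deciding test nor the comparison family stated. That much is read directly from the SAP and needs no assumption.

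The power cost is real under each reading of Bonferroni examined, but its size is conditional. At n = 10, two-sided, with an assumed dz of 1.0, it runs from about 5 points (two comparisons, pooled error, sphericity) to about 20 (three comparisons, paired errors). It should be quoted as a range and not as a property of a plan that states no effect size or power. In a feasibility pilot, the main practical harm is uncertainty over which result answers Question 3. The change is worth making because it is cheap and brings the test into line with the plan's own objective.

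**What to change.** Amend SAP 2.2.2 as follows:

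- Name the mean of the Pre-Tests to Post-Test as the primary paired contrast, at two-sided 0.05, with its estimate and unadjusted 95% confidence interval.
- Test the Pre mean to Follow Up at two-sided 0.05 only if the first contrast is significant. This fixed sequence controls the error rate across those two tests without splitting alpha.
- Report Post-Test versus Follow Up as an estimate with its interval, without a formal test.
- Keep the repeated measures ANOVA and its F value as supportive.

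If the ANOVA is to remain the main analysis, the minimum is to state which result decides Question 3 and which comparisons Bonferroni covers.

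The cost is SAP wording only, with no new data or participants. The downside is that Follow Up cannot be formally claimed if the Post-Test contrast fails, and Post-Test versus Follow Up has no formal test.
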